- ^f Baseline sample, not a screening sample; results not needed prior to randomization.
- ^g If the urine pregnancy test is positive or indeterminate, a quantitative serum β -hCG will be performed by the central laboratory for confirmation.
- ^h On Day 1, a negative urine pregnancy test is required before the participant receives IMP.
- ⁱ For a subset of 20 participants, PK and NLF samples will be collected at 24 to 72 hours after the Day 1 AZD7442 dose.
- ^j For a subset of 20 participants, PK and NLF samples will be collected at Day 11 (± 3 days).
- ^k When test supplies are available, sampling should be performed.
- ^l Includes monitoring participants for at least one hour postdose, checking injection sites, and monitoring for hypersensitivity (including anaphylaxis). See Section 8.2.5 for required safety monitoring.
- ^m If local facilities or local regulations do not allow for an RTM visit, an In-person visit can be performed.
- ⁿ Targeted physical examination per investigator discretion will include areas suggested by medical history, vulnerable conditions and reported clinical complaints during the study visit and may require height and weight.
- ^o Monthly contact with participants to remind them to present to the study site for SARS-CoV-2 testing if they have qualifying symptoms. The Investigator will enquire about any COVID-19 symptoms from previous 30 days and other adverse events.

Note: In agreement with the Sponsor, In-person visits may be replaced with home or mobile visits if required to protect participants from COVID-19 infection and as per Investigator's discretion provided they are operationally feasible.

ADA, antidrug antibody; AE, adverse event; AESI, adverse event of special interest; β -hCG, beta-human chorionic gonadotropin; COVID-19, coronavirus disease 2019; D, day; ECG, electrocardiogram; EoT, End of Treatment; FSH, follicle-stimulating hormone; IM, intramuscular; IMP, investigational medicinal product; M, month; nAb, neutralizing antibody; NLF, nasal lining fluid; NP, nasopharyngeal; PD, pharmacodynamics; PID, participant identification; PK, pharmacokinetics; Q3M, every 3 months; RT-PCR, reverse transcriptase polymerase chain reaction; SAE, serious adverse event; SARS-CoV-2, severe acute respiratory syndrome-coronavirus-2; TM, telemedicine; WOCBP, women of childbearing potential.

Table 2 Schedule of Activities: Treatment Period – Arm B (AZD7442 Q6M)

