Week (Month)	-	-	1	4	13 (3M)	26 (6M)	27	30 (7M)	39 (9M)	52 (12M)	53	65 (15M)	
Window (days)	-	-	± 3	± 5	± 7	± 7	± 3	± 5	± 7	± 7	± 3	± 15	
P = In-Person Visit RTM = Remote TM Visit ⁿ	P	P	RTM/ P ⁿ	P	P	P	RTM/ P ⁿ	P	P	P	RTM/ P ⁿ	P	
Nasopharyngeal samples													
Documented negative SARS-CoV-2 RT-PCR test from NP specimen taken ≤ 3 days before Day 1 ^d OR SARS-CoV-2 rapid antigen test	X ^e												8.2.4
SARS-CoV-2 RT-PCR (central laboratory) (predose)		X ^f											8.2.4
Urine samples													
Pregnancy test – urine (WOCBP only) ^g ; (predose on days of IMP administration)	X	X ^h		X	X	X		X	X	X		X	5.3, 8.2.4, 8.3.9.1
Urinalysis (predose on days of IMP administration)		X			X	X			X	X		X	8.2.4
PK, PD, ADA assessments													
Serum sample for AZD7442 PK assessment (predose on days of IMP administration unless otherwise noted)		D1 ⁱ , D3 (±1d)) ^j	D11 (±3d) ^k	X	X	X		X	X	X		X	8.5.1
Serum sample for AZD7442 ADA assessment (predose on days of IMP administration)		X		X	X	X		X	X	X		X	8.5.2.1
Serum sample for SARS-CoV-2 nAbs assessment (predose on days of IMP administration)		X		X	X	X		X	X	X		X	8.5.3.1

Table 2 Schedule of Activities: Treatment Period – Arm B (AZD7442 Q6M)

Period	Screen ^a	Treatment (Days 1-456)										EoT	For details, see Section
Day (* = IMP dosing day)	-7 to 1	1*	8	29	92	183*	190	D212	274	365*	372	456	
Week (Month)	-	-	1	4	13 (3M)	26 (6M)	27	30 (7M)	39 (9M)	52 (12M)	53	65 (15M)	
Window (days)	-	-	± 3	± 5	± 7	± 7	± 3	± 5	± 7	± 7	± 3	± 15	
P = In-Person Visit RTM = Remote TM Visit ⁿ	P	P	RTM/ P ⁿ	P	P	P	RTM/ P ⁿ	P	P	P	RTM/ P ⁿ	P	
NLF sample for mucosal response assessments ^l (predose on days of IMP administration unless otherwise noted)		D1 ⁱ , D3 (±1d)) ^j	D11 (±3d) ^k	X	X	X		X	X	X		X	8.5.2.3
Serum sample for SARS-CoV-2 serology (anti-nucleocapsid) testing (predose on days of IMP administration)		X		X	X	X		X	X	X		X	8.5.2.2
IMP Administration													
Arm B: AZD7442 administration		X				X				X			6.1, 6.2
Postdose safety monitoring ^m		X	X			X	X			X	X		8.2.5
Safety assessments													
AEs/SAEs/AESIs	SAEs only	←-----→										8.3	
Monthly contact between visits													
Monthly telephone/email/text contacts - monitoring for COVID-19 symptoms and safety ^p													8.1.1, 8.3

^a Screening activities may be collected over more than one visit if necessary; if screening and dosing occur at the same visit, only one evaluation is required, unless otherwise specified.

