^b Day 1 (AZD7442 IV administration): Perform vital signs (including pulse oximetry) within 15 minutes prior to the start of infusion, every 15 minutes (± 5 minutes) during the infusion, and 15 minutes (± 5 minutes) after end of infusion.
 Days 183 and 365 (AZD7442 IM administration): Perform vital signs (including pulse oximetry) predose (within 15 minutes prior to first injection) and postdose (15 minutes [± 5 minutes] after both injections are complete).

- ^c FSH will be analyzed at screening to confirm postmenopausal status only in women < 50 years of age who have been amenorrhoeic for ≥ 12 months. Until FSH is documented to be within menopausal range, the participant is to be considered of childbearing potential. For women aged ≥ 50 years, postmenopausal is defined as having a history of ≥ 12 months' amenorrhea prior to Day 1, without an alternative cause, following cessation of exogenous sex-hormonal treatment.
- ^d This test is not performed as part of the clinical study but must be available prior to enrollment.
- ^e If a documented (negative) SARS-CoV-2 RT-PCR test is not available at screening, a SARS-CoV-2 rapid antigen test will be performed. Either test must be negative before dosing (see inclusion criteria in Section 5.1).
- ^f Baseline sample, not a screening sample; results not needed prior to randomization.
- ^g If the urine pregnancy test is positive or indeterminate, a quantitative serum β -hCG will be performed by the central laboratory for confirmation.
- ^h On Day 1, a negative urine pregnancy test is required before the participant receives IMP.
- ⁱ For all participants, the PK and NLF samples will be collected postdose within 30 minutes after the end of infusion on Day 1.
- ^j For a subset of 20 participants, PK and NLF samples will be collected at 24 to 72 hours after the Day 1 AZD7442 dose.
- ^k For a subset of 20 participants, PK and NLF samples will be collected at Day 11 (± 3 days).
- ^l When test supplies are available, sampling should be performed.
- ^m Includes monitoring participants for at least one hour postdose, checking injection sites, and monitoring for hypersensitivity (including anaphylaxis), and infusion-related reactions (applicable for Day 1 IV administration). On Day 1, the minimum of one hour postdose monitoring will start at the end of the IV infusion. See Section 8.2.5 for required safety monitoring.

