Day 11	11	7 – 19 [subset of 20 participants, PK and NLF assessment]
Day 29	29	20 – 60 [subset of 20 participants, PK and NLF assessment] 2 – 60 [otherwise]
Day 92	92	61 - 106
Day 121	121	107 - 152
Day 183	183	153 - 197
Day 212	212	198 - 242
Day 274	274	243 - 319
Day 365	365	320 - 410
Day 456	456	≥411

Arm B

Visit	Day Relative to First Dose	Visit Window (Study Day)
Day 1, Post-dose	1	1, > 1 st IMP dose time
Day 3	3	2 – 6 [subset of 20 participants, PK and NLF assessment]

Visit	Day Relative to First Dose	Visit Window (Study Day)
Day 11	11	7 – 19 [subset of 20 participants, PK and NLF assessment]
Day 29	29	20 – 60 [subset of 20 participants, PK and NLF assessment] 2 – 60 [otherwise]
Day 92	92	61 - 137
Day 183	183	138 - 197
Day 212	212	198 - 242
Day 274	274	243 - 319
Day 365	365	320 - 410
Day 456	456	≥411

Table 5: Analysis windows for cardiac/thrombosis biomarkers

Visit	Day Relative to First Dose	Visit Window (Study Day)
Day 1	≤ 1	≤ 1
Day 29	29	2 - 60
Day 92	92	61 - 137
Day 183	183	138 - 228
Day 274	274	229 - 319
Day 365	365	320 - 410
Day 456	456	411 - 592
Day 729 (Follow-up)	729	≥593

Table 6: Analysis windows for clinical chemistry, hematology, coagulation, and urinalysis

Visit	Day Relative to First Dose	Visit Window (Study Day)
Day 1	≤ 1	≤ 1
Day 92	92	2 - 137
Day 183	183	138 - 228
Day 274	274	229 - 319
Day 365	365	320 - 410
Day 456	456	411 - 592
Day 729 (Follow-up)	729	≥593

Table 7: Analysis windows for Vital signs

Arm A

Visit	Day Relative to First Dose	Visit Window (Study Day)
Screening	<1	<1
Day 1, Pre-dose	1	1, ≤ 1 st IMP dose time
Day 1, Post-dose	1	1, > 1 st IMP dose time
Day 29	29	2 - 60
Day 92, Pre-dose	92	61 – 106, ≤ 2 nd IMP dose time
Day 92, Post-dose	92	61 – 106, > 2 nd IMP dose time
Day 121	121	107 - 151
Day 183, Pre-dose	183	152 – 197, ≤ 3 rd IMP dose time
Day 183, Post-dose	183	152 – 197, > 3 rd IMP dose time
Day 212	212	198 - 242
Day 274, Pre-dose	274	243 – 319, ≤ 4 th IMP dose time
Day 274, Post-dose	274	243 – 319, > 4 th IMP dose time
Day 365, Pre-dose	365	320 – 410, ≤ 5 th IMP dose time
Day 365, Post-dose	365	320 – 410, > 5 th IMP dose time
Day 456	456	411 - 592
Day 729 (Follow-up)	729	≥593

Arm B

Visit	Day Relative to First Dose	Visit Window (Study Day)
Screening	<1	<1
Day 1, Pre-dose	1	1, ≤ 1 st IMP dose time
Day 1, During Dose, 15 mins	1	>1 st IMP dose time - ≤ 22 minutes 30 seconds post 1 st IMP dose time

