$$\hat{\rho}_i = \frac{Cov_{subject(2,1)_i} + Cov_{visit(subject)(2,1)_i}}{\sqrt{((Cov_{subject(1,1)_i} + Cov_{visit(subject)(1,1)_i}) \times (Cov_{subject(2,2)_i} + Cov_{visit(subject)(2,2)_i}))}}$$

where Cov represents the covariance term at participant level (subject) and visit nested within participant [visit(subject)]. The same correlation estimate, $\hat{\rho}$ will be fit to the full data (i.e. not resampling) and the mean bias adjusted factor will be derived as

$$\hat{b} = \frac{\sum_{i=1}^n (\hat{\rho}_i - \hat{\rho})}{n},$$

where n is the number of converged models. The median, 2.5th and 97.5th percentiles will be taken over $\hat{\rho}_i - \hat{b}$ to give the bias-adjusted bootstrapped correlation coefficient and 95% CI. Convergence (%) will be defined as percentage of converged models with respect to the number of bootstraps run. This correlation analysis is based on paired quantifiable records from both PK and nAb samples (on the same sample collection date). Samples from illness visits or samples having values <LLOQ are also to be excluded.

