4.2.2.4 Primary Analysis of Secondary Endpoints

4.2.2.4.1 Pharmacokinetics Data

PK analysis will be based on actual treatment in the PK Analysis Set.

If a participant has any protocol deviation which is identified as a record-level exclusion for the PK analysis in Table 5 of the most recent version of the PDMP, then the PK samples of both compounds collected after the date of deviation and the corresponding derived total concentrations for AZD7442 will be excluded from the analyses.

Due to the change in dosing schedules between CSP V3.0 (dated 09 December 2022) and CSP V4.0 (dated 06 June 2023), there may be visits with a mixture of participants who received and participants who did not receive IMP in previous visit. Therefore, any PK samples from participants who did not receive IMP according to the SoA of CSP V3.0, irrespective of the visit date being before or after the effective date of CSP V4.0 implementation, will be excluded from analyses at all subsequent visits.

PK assessments scheduled for collection pre-dose, but instead collected post-dose at a visit where dosing is done, will be excluded from the analyses. Similarly, PK assessments scheduled for collection post-dose, but collected pre-dose will also be excluded from the analyses.

Individual AZD7442 (AZD8895 and AZD1061) serum concentrations data will be listed and tabulated by mAb component, along with descriptive statistics for the PK analysis set for each treatment group.

Figures of serum concentrations by mAb component and treatment group will also be presented. The figures will include the subset of 20 participants with additional PK measurements.

Potential correlation between PK exposure and safety response may optionally be explored. PK analysis may be performed by the Sponsor and reported in a separate report. The analysis is not covered in this SAP.

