4.2.2.4.2 SARS-CoV-2 Neutralizing Antibodies

SARS-CoV-2 nAb analysis will be based on actual treatment in nAb Evaluable Analysis Set. Two (2) assays will be used to provide titers for authentic virus and pseudovirus nAb.

If a participant has any protocol deviation which is identified as a record-level exclusion for the immunogenicity analysis in Table 5 of the most recent version of the PDMP, then their SARS-CoV-2 nAb samples collected after the date of deviation will be excluded from the analyses.

Due to the change in dosing schedules between CSP V3.0 (dated 09 December 2022) and CSP V4.0 (dated 06 June 2023), there may be visits with a mixture of participants who received and participants who did not receive IMP in previous visit. Therefore, any SARS-CoV-2 nAb samples from participants who did not receive IMP according to the SoA of CSP V3.0, irrespective of the visit date being before or after the effective date of CSP V4.0, will be excluded from analyses at all subsequent visits.

SARS-CoV-2 nAb assessments scheduled for collection pre-dose, but instead collected post-dose at a visit where dosing is done, will be excluded from the analyses.

For participants who receive a COVID-19 vaccine after the first dose of IMP, data collected after receipt of the vaccine will also be excluded. Furthermore, for participant who receive a positive SARS-CoV-2 RT-PCR (defined in Section 4.2.3.4.1), data collected after infection will also be excluded, except in the case that SARS-CoV-2 nAb samples were collected during an illness visit.

Descriptive statistics for titer and fold rise will include number of participants, geometric mean, geometric standard deviation (gSD), 95% confidence interval (CI), minimum and maximum. This will be reported separately for nAbs collected during treatment period and illness visits (the illness visits where the series corresponds to positive RT-PCR test, as defined in Section 4.2.3.4.1, will be used in the summary).

A scatter plot of log₂ transformed titers with log₂ transformed serum concentration for each treatment arm, along with the bias-adjusted bootstrapped correlation coefficient, 95% CI and convergence (%) (see Section 4.2.2.2.1).

Summaries will also be split by the previous COVID-19 vaccination status (as defined in Section 4.1.5.1). Samples from 2 separate assays will be analysed using the same methods as described here.

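### The titer–concentration correlation pairs samples by date alone, so in Arm B a quantifiable Day 1 pre-dose titer is matched with the end-of-infusion concentration

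*SAP*

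**What the plan says.** SAP 4.2.2.2.2 estimates, separately in each arm, the correlation between log2 nAb titer and log2 serum concentration. It uses a bivariate mixed model with a participant-level bootstrap. The data entering it are defined so: "This correlation analysis is based on paired quantifiable records from both PK and nAb samples (on the same sample collection date". The only further filter in that section is "Samples from illness visits or samples having values <LLOQ are also to be excluded". Nothing there refers to time relative to dosing.

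Sampling times are in Protocol 1.3, Table 2 (Arm B):

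- nAb: "Serum sample for SARS-CoV-2 nAbs assessment (predose on days of IMP administration"; Day 1 is marked.
- PK, Day 1: "For all participants, the PK and NLF samples will be collected postdose within 30 minutes after the end of infusion on Day 1".

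The SAP's only Arm B Day 1 window for serum PK is "Day 1, Post-dose" (SAP 3.3.2, Table 4).

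Two record-level rules deal with timing. SAP 4.2.2.4.2: "SARS-CoV-2 nAb assessments scheduled for collection pre-dose, but instead collected post-dose at a visit where dosing is done, will be excluded from the analyses". SAP 4.2.2.4.1 drops PK samples planned pre-dose but drawn after dosing, and also the reverse: "PK assessments scheduled for collection post-dose, but collected pre-dose will also be excluded from the analyses".

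In Arm A (Protocol 1.3, Table 1) there is no Day 1 PK sample. The earliest is "For a subset of 20 participants, PK and NLF samples will be collected at 24 to 72 hours after the Day 1 AZD7442 dose".

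**The concern.** The coefficient and scatter plot are meant to show how neutralising titer follows drug concentration. A titer drawn before the first dose contains no study drug. Matching it with a concentration measured just after a 1200 mg infusion says nothing about that relation. It places a point at high concentration and, if baseline titers are lower than on-drug titers, at low titer, against the expected trend.

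The timing exclusions do not help. They remove samples drawn on the wrong side of the dose relative to schedule. Here the schedule itself puts the two samples on opposite sides, so compliance guarantees the mismatch.

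At stake is a misleading descriptive result for one arm: a weaker apparent link between titer and exposure than the valid pairs would show.

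**Working it through.** **1. Which same-date pairs exist in Arm B**

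| Visit | nAb sample | PK sample | Same side of dose? |
|---|---|---|---|
| Day 1 | pre-dose | after infusion | No |
| Days 183, 365 (planned dosing days) | pre-dose | pre-dose | Yes |
| Days 29, 92, 212, 274, 456 | no dose that day | no dose that day | Yes |

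Day 1 is the only mismatch. The below-LLOQ filter removes it for participants without a quantifiable baseline titer. Some can have one: Protocol 6.5.1 admits previously vaccinated participants, and Protocol 5.2 (criterion 1) does not exclude prior infection. The share is not stated.

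**2. Why the model does not absorb it**

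The only fixed effect is the response identifier. With no visit effect, the Day 1 deviations enter the covariances that form the SAP's coefficient.

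The bootstrap adjustment is b = mean(ρᵢ) − ρ, where ρ is the full-data estimate and ρᵢ the resample estimates. So mean(ρᵢ − b) = ρ. The adjusted distribution is centred on the full-data estimate, which contains the mismatched pairs. The interval therefore offers no protection. This is algebra; the bootstrap itself was not run.

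**3. Size, for illustration**

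The documents give no correlation to reproduce. Two inputs come from the Protocol: 100 Arm B participants (4.1) and a half-life of about 90 days (2.2). The rest are assumptions:

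- one compartment; IM bioavailability 0.7; absorption half-life 5 days;
- log2 titer rises one for one with log2 concentration;
- log2 SDs: concentration 0.4 between participants and 0.3 residual; titer a further 0.6 and 0.6; baseline titer 1.5;
- valid pairs at Days 29, 92, 183, 212, 274 and 365;
- g = how far the mean baseline titer lies below the mean on-drug titer (2, 4 or 6 log2);
- q = share with a quantifiable baseline titer (0 to 100%).

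Mean log2 concentrations, in dose units, are 9.92, 9.22, 8.21, 9.19, 8.52 and 7.51 (mean 8.76, variance V = 0.610). Day 1 is log2(1200) = 10.23, which is D = 1.47 above that mean.

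*Valid pairs only.* Concentration variance = 0.610 + 0.4² + 0.3² = 0.860. Titer variance = 0.860 + 0.6² + 0.6² = 1.580. Covariance = 0.860. Then ρ = 0.860/√(0.860 × 1.580) = 0.74.

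*With the Day 1 pair.* Let w = 6/(6+q) be the weight of valid pairs and d = 1 − w that of Day 1 pairs.

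- Concentration variance = wV + wdD² + 0.25
- Titer variance = wV + wdg² + 0.97w + 2.25d
- Covariance = wV − wdDg + 0.25w

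Here 0.25 = 0.4² + 0.3², 0.97 = 0.25 + 0.72 and 2.25 = 1.5². For q = 50% and g = 4: w = 0.923, d = 0.077; the variances are 0.967 and 2.768, the covariance 0.377; ρ = 0.377/√(0.967 × 2.768) = 0.23.

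Fitting the SAP's model by maximum likelihood to simulated data (25 replicates per cell) and applying the SAP's formula gives:

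| q | g = 2 | g = 4 | g = 6 |
|---|---|---|---|
| 0% | 0.74 | 0.74 | 0.74 |
| 10% | 0.66 | 0.59 | 0.52 |
| 25% | 0.56 | 0.43 | 0.30 |
| 50% | 0.44 | 0.23 | 0.07 |
| 75% | 0.33 | 0.10 | −0.05 |
| 100% | 0.26 | 0.01 | −0.13 |

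The hand formula agrees with every cell to within 0.02.

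**The case against.** **Pairing might be by visit.** The model's residual covariance is defined within visit, and SAP 3.3.2 labels the baseline nAb record differently from the Arm B Day 1 PK record. If records had to match on visit label as well as date, the Day 1 titer would have no partner. But the SAP states no such condition; the only matching criterion it gives is the date. If the labels merely serve as the visit variable, both records stay in the data in separate blocks, which is not a valid analysis either.

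**The size is not known.** This stands. The documents give neither the quantifiable share nor the gap. Protocol 4.1 describes a population unable to respond adequately to vaccination, which points to a lower share. LLOQ censoring also links the two quantities (lower baseline titers are less often quantifiable), whereas the table varies them independently. Nor does the simulation model the participant's own antibody persisting after dosing, so 0.74 may be too high. A reader might infer that the coefficient falls to zero or below. The documents do not support that: in the table it needs both a high share and a large gap.

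**The consequence is limited.** This also stands. The correlation is not an endpoint, no hypothesis is tested, and mispaired points may show as a cluster on the plot. A reader might also infer that the artefact explains any Arm A versus Arm B difference. No such comparison is planned, and the arms also differ in route, dose, interval and visits, all of which affect a correlation.

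**Conclusion.** The stated rule is wrong as written for Arm B. It admits a pair whose two members lie on opposite sides of the first dose, and no other rule in the SAP removes it. The effect is nil only if no such pair enters. The downward direction rests on baseline titers lying below on-drug titers.

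Under the assumptions above, the loss from 0.74 is 0.08 to 0.22 at a 10% share and 0.30 to 0.67 at 50%. These figures illustrate sensitivity; they do not predict the trial's result. With two nAb assays, each with its own quantifiable share, the effect may differ between them.

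The reach is confined to the Arm B coefficient, its interval and the scatter plot. Safety, ADA incidence, GMT, GMFR and the serum concentration summaries do not use these pairs. The point is worth correcting because the fault is clear and the remedy cheap, not because a main conclusion is in danger.

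**What to change.** In SAP 4.2.2.2.2, require both samples of a pair to come from the same date and from the same side of any IMP dose given that day. State that the Arm B Day 1 combination (pre-dose nAb, post-dose PK) is excluded from both the correlation and the scatter plot. Say also what the visit variable in the model is, so that the visit labels leave no second reading.

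Do not achieve this by limiting pairs to scheduled visits after Day 1. SAP 3.3.3 lets unscheduled and early discontinuation measurements contribute to summaries. The Early Discontinuation visit collects both PK and nAb samples (Protocol 1.3, Table 3) and, after the early termination, replaces the Day 365 or Day 456 visit for some participants. Those pairs are valid and should stay.

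The cost is a sentence or two of SAP text and one programming filter. No valid pair is lost and no new data are needed.
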